### 3. STUDY DESIGN

A performance validation pilot of the CPM#1 device in healthy volunteers. There will only be one study arm, no comparator, and no randomization. Participants participate in one 60-minute study visit (one session) and no follow-up is planned. The total study duration is three months.

### 4. STUDY POPULATION

#### 4.1 Population (base)

35 Healthy volunteers recruited among personnel affiliated with Máxima MC.

#### 4.2 Inclusion criteria

- $\geq 18$  years
- Proficient in speaking and reading Dutch

#### 4.3 Exclusion criteria

- Presence of complaints suggestive of CECS, previously diagnosed with CECS or previous positive ICPM
- History of surgery or other trauma which penetrated the fascia of the leg
- Other concurrent limb pathologies or anomalies amongst others:
  - Peripheral arterial or venous disease
  - Muscle disorders, diabetes mellitus, peripheral neuropathies
- Unable to exercise for five minutes
- Open wound or painful bruise less than one week ago at site of measurement

#### 4.4 Sample size calculation

As data on this device are scarce, a pragmatic sample size rationale is pursued based on previous studies that were made available to us by the company. Moreover, this study is not aimed at hypothesis testing, rather, we aim to estimate the ICC with certain precision. With the predecessor of CPM#1 it has been shown that an  $ICC \geq 0.75$  is achievable and thus demonstrated a good inter-observer reliability.

[figure not shown]
Measuring the left and right m. tibialis anterior in two directions, an expected  $ICC = 0.8$  (based on bench tests) and a one-sided 95% target confidence interval width of 0.05 based on three observers, a sample size of 140 is required. Since we measure 4 'samples' per participant (each leg the m.tibialis anterior at two different approaches, see section 5.1), we aim to include 35 healthy volunteers (140:4). We do not include dropouts in our calculation since we perform only one 90 minute session without follow-up. Participants who do not complete the

measurements will be replaced for new inclusions, such that we will have a complete data set of 35 participants in the end.

To power for the measurement directly after exercise, using dependent sample T-test with an expected effect size of 0.4 (based on results from bench test), an  $\alpha$  of 0.05 and power ( $\beta-1$ ) of 0.9, we would require 68 samples. Since the strict timing of the measurements after exercise only allows the measurement of one sample (one compartment using one approach), all participants will undergo two exercise sessions ( $2 \times 35 = 70$ ).

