## 5. TREATMENT OF SUBJECTS

Healthy subjects are not subjected to any type of treatment besides a lower leg muscle compressibility measurement. A summary of the measurements is given in figure 1.

*Figure 1: Summary of measurements. A total of 35 healthy volunteers will be included, who all will undergo rest measurements performed by three observers. These three observers will measure the anterior compartment (m. tibialis anterior) four times at four different locations (Right leg with tibial notch as internal landmark, right leg with interosseous membrane as internal landmark, left leg with tibial notch as internal landmark, and left leg with interosseous membrane as internal landmark). All healthy volunteers will then subsequently perform a treadmill exercise twice. After the first time, the right leg with tibial notch as internal landmark will be measured immediately, 1-minute, and at 5-minutes post exercise. After the second exercise the left leg will be measured immediately, at 1-minute, and at 5-minutes post exercise. Randomization will determine whether the right or left leg is measured first.*

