## 8. METHODS

### 8.1 Study parameters/endpoints

#### 8.1.1 Main study parameter/endpoint

Inter-observer variance of compressibility among three observers using inter-class correlation coefficients (two-way random effects, single observer, absolute agreement).

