## 10. STATISTICAL ANALYSIS

Intra-class correlation coefficients will be calculated as indicated below and described using 95% confidence intervals.

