### 10.1 Primary study parameter(s)

The primary endpoint of inter-observer variability will be the intraclass correlation coefficient (ICC) of agreement between three observers, four sites per subject, and four repetitions per measurement. The ICC will be assessed using a two-way random effects model. Both observers and subjects will be included as random effects. The first measurement for each location will be taken from every observer to calculate the ICC. Apart from that, the ICC will be measured using the average of the four repetitions of ratings, to estimate the effect on the ICC of repetitive measurements. “Good reliability” classification will be reached if the lower bound of the computed ICC confidence interval does not fall below 0.75.

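### The stated 0.05 precision counts 35 participants × 4 sites as 140 independent targets, and section 10.1 does not fix the unit of analysis

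*Combined protocol and SAP*

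**What the plan says.** Section 4.4 states the purpose of the primary sample size: "we aim to estimate the ICC with certain precision". With an expected ICC of 0.8 it asks for "a one-sided 95% target confidence interval width of 0.05 based on three observers, a sample size of 140 is required". It then notes that each participant supplies four samples, and concludes "we aim to include 35 healthy volunteers (140:4" (140 divided by 4). No within-participant correlation, design effect or observer variance is given.

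The Figure 1 legend in section 5 says that the three observers "will measure the anterior compartment (m. tibialis anterior) four times at four different locations": the tibial notch and the interosseous membrane, in each leg. Section 5.1 adds that the membrane landmark appears to be the less variable of the two.

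Section 8.1.1 defines the primary ICC as "two-way random effects, single observer, absolute agreement". Section 10 says that ICCs will be "described using 95% confidence intervals". Section 10.1 says "Both observers and subjects will be included as random effects" and "The first measurement for each location will be taken from every observer to calculate the ICC". It mentions four sites per subject, and it grants the good-reliability classification when the lower confidence limit is at least 0.75.

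**The concern.** Dividing 140 by 4 treats two landmarks in each of two legs of one person as four unrelated targets. Values from one person are likely to resemble each other, so independence is the assumption that needs a reason, and none is given.

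Precision is the only basis for the primary sample size, and the reliability verdict rests on the lower confidence limit. Section 10.1 leaves three analyses open, and they behave differently:

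- **140 pooled rows:** the interval keeps about the planned width, but covers too rarely when sites correlate.
- **35 rows per site:** the interval is valid, but about twice as wide as planned.
- **Sites nested in participants:** the interval is honest, and its width depends on the correlation.

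If the choice is not written down, it can be made after the data are seen.

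**Working it through.** **Inputs from the plan.** ICC 0.8, k = 3 observers, width 0.05, 140 targets, four sites per participant, 35 participants (section 4.4); random observers and absolute agreement (8.1.1, 10.1); lower-limit rule of 0.75 (10.1).

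**Inputs not in the plan.** The correlation r between true site values within a participant (assumed 0.3 to 0.9), and observer variance as a share of total variance (zero in the main check).

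**Step 1: reproduce 140.** The plan names no formula. The standard large-sample precision formula for an ICC, with full width w, is

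n = 8 z² (1 − ICC)² [1 + (k − 1) ICC]² / [k(k − 1) w²] + 1.

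With ICC = 0.8, k = 3 and w = 0.10 (0.05 each side):

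- z = 1.96: 8 × 3.8416 × 0.04 × 6.76 / (6 × 0.01) + 1 = 139.5, rounded up to 140.
- z = 1.645: 98.5, rounded up to 99.

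A full width of 0.05 gives 555 (z = 1.96) or 392 (z = 1.645). So 140 is the half-width of a two-sided 95% interval on independent targets. The same formula gives a half-width of 0.0499 at n = 140 and 0.101 at n = 35.

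**Step 2: clustering, closed form.** The correlation between site means over three observers is ρ = r × 0.8 / (0.8 + 0.2/3). The variance inflation for the estimated ICC is about D = [(1 + 3ρ²) + 0.5] / 1.5, and the half-width is 0.0499 × √D. D is 1.15 / 1.43 / 1.84 / 2.38 at r = 0.3 / 0.5 / 0.7 / 0.9. The familiar factor 1 + (m − 1)r, with m sites per participant, would overstate the loss, because it applies to a mean and not to an ICC.

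**Step 3: simulation of 35 × 4 × 3 data.** 10,000 runs per setting, no observer variance, pooled 140-row absolute-agreement ICC with its usual F-based 95% interval. The true half-width is 1.96 × the SD of the estimates.

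| r | Half-width, closed form | True half-width, simulated (ICC 0.80) | Coverage of pooled interval | False good verdicts (true ICC 0.75) |
|---|---|---|---|---|
| 0 | 0.050 | 0.051 | 95% | 2.5% |
| 0.3 | 0.054 | 0.054 | 93% | 2.8% |
| 0.5 | 0.060 | 0.061 | 90% | 4.1% |
| 0.7 | 0.068 | 0.070 | 85% | 6.1% |
| 0.9 | 0.077 | 0.082 | 79% | 8.0% |

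The half-width that the pooled interval reports stays near 0.051 throughout, so the output would not reveal the problem.

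**Step 4: chance of meeting the 0.75 rule at a true ICC of 0.80.** Pooled rows: 0.41 to 0.44 at any r. One site alone: 0.15. With a participant-level jackknife, which respects clustering, it is about 0.34 at r = 0.3 and 0.26 at r = 0.5, and lower beyond that. The jackknife values depend on the method.

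**Step 5: literal one-sided reading.** The arm is 0.0419 × √D, which is 0.045 / 0.050 / 0.057 / 0.065 at r = 0.3 / 0.5 / 0.7 / 0.9.

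**Step 6: landmark.** At true ICC 0.75, r = 0.5 and no observer variance, a mean difference between landmarks of 0.5 total SD raises false good verdicts in the pooled analysis from about 4% to 9%. The size of any such difference is also not in the documents.

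**Step 7: observer variance (independent sites).** If observers account for 2% or 4% of total variance, the median distance from estimate to lower limit is about 0.06 or 0.08, against 0.054 with none.

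**The case against.** The strongest reply is that section 4.4 calls the sample size pragmatic and the study is a small pilot not aimed at hypothesis testing. That is a good reason not to enlarge it. It does not make the precision statement correct, and section 10.1 still sets a pass mark on the confidence limit.

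The size of the effect is wholly assumed. At r = 0.3 it is small (0.054 against 0.05), and the larger figures need r of 0.7 or more. This stands: the direction is firm, the magnitude is not.

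Three stronger readings are tempting, and the documents do not support them:

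- **The 0.05 fails as soon as sites correlate at all.** Section 4.4 says one-sided. Taken literally, 0.05 would hold up to about r = 0.5 with no observer variance. That reading does not produce 140, but the two-sided reading is inferred from an unnamed formula, and a figure beside the calculation is not shown in the text available.
- **The calculation ignores the observers.** It uses three observers. What appears to be absent is a term for observer variance, and that too is inferred from the numerical match.
- **The analysis neglects observer variance.** Sections 8.1.1 and 10.1 already specify a random-observer absolute-agreement ICC, whose usual interval reflects that variance. With independent sites, its coverage is about 95% at a 2% observer share and about 93% at 4%. The extra width comes from having only three observers, and rewording cannot remove it.

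**Conclusion.** The concern holds for clustering and for the open unit of analysis. The stated 0.05 precision, read in the only way that yields 140, needs independent sites. With r from 0.3 to 0.9 and no observer variance, 35 × 4 sites give a true half-width of about 0.054 to 0.082 at ICC 0.80. An interval computed on 140 pooled rows as if independent then covers about 93% to 79%, with about 3% to 8% false good verdicts at true ICC 0.75 against a nominal 2.5%. Analysis of one site at a time gives about 0.10. The absence of a design effect is explicit in the division by four and does not depend on the inferred formula. Observer variance is a caveat: it widens the interval further. A reader might infer that the study is too small or must recruit more, but that does not follow from a pragmatic pilot. What needs correcting is the precision claim and the analysis specification.

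**What to change.** Keep 35 participants and change two places.

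1. **Section 4.4.** Replace the one-sided width wording with a half-width of 0.05 for a two-sided 95% confidence interval, and state that this assumes independent sites and no observer variance. Then give the expected half-width, and the chance of meeting the 0.75 rule, for 35 participants × 4 correlated sites × 3 random observers, over a stated range of site correlation and observer variance. Compute both with the interval method named in 10.1.
2. **Section 10.1.** State the unit of analysis, for example: *The ICC is estimated from the first measurements of three observers at four sites in 35 participants, with landmark as a fixed effect; the 95% CI accounts for sites clustered within participants and treats observers as random.* Reporting the ICC separately by landmark is an alternative; the two legs of a participant then remain clustered. Do not take the interval from a 140-row independence formula.

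**Cost.** No extra participants or measurements, and a somewhat more complex analysis. The stated precision and the chance of a good-reliability verdict become less favourable. With three observers the price of an interval that keeps them random can be high: in one such method, a generalised confidence interval, the median half-width was 0.06 to 0.085 with no observer variance and 0.16 to 0.18 at a 2% share, which makes a lower limit of 0.75 unlikely at a true ICC of 0.80. A participant-level jackknife is narrower, but it holds observers fixed and so does not meet the proposed wording. The sponsor should settle this trade-off before data collection.

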### 5.1 Investigational product/treatment

All 35 healthy subjects will undergo four times four measurements in rest (m. tibialis anterior of both legs, using two different internal landmarks). Although the 'tibial notch' between the interosseous membrane and the tibial bone was previously suggested as the optimal landmark, recent data from our department suggest that the middle of the interosseous membrane is less variable. These four times four measurements in rest will each be done by three observers.

To measure the effect of exercise, compressibility will be measured immediately, one minute, and five minutes after a standard treadmill exercise at just one leg. The treadmill exercise and the corresponding measurements will be performed twice to include measurements of both legs. The measurements after exercise will be performed by only one observer.

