### 8.3 Study procedures

This outpatient study will be conducted on 35 healthy volunteers. Participants will be placed comfortably in supine position. Measurements of compartment compressibility will be performed for each participant on both legs using the CPM#1. Exercise by means of a treadmill will be performed after all rest measurements have been performed.

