### 10.2 Secondary study parameter(s)

The secondary endpoint of intra-observer variability will be the intraclass correlation coefficient (ICC) of agreement within three observers, four sites per subject, and four repetitions per measurement. The ICC will be assessed using a two-way random effects model. Both subjects and repetitions will be included as random effects. The repeated measures will be analysed for each observer separately and this agreement serves to address differences between observers. “Good reliability” classification will be reached if the lower bound of the computed ICC confidence interval does not fall below 0.75

The second secondary endpoint is the comparison between post-exercise (immediate, one minute, and five minutes) compressibility and rest compressibility. This will be analysed using a dependent sample t-test.

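### The 90% power for the exercise comparison counts two legs from each of 35 people as 70 independent pairs, and section 10.2 does not allow for the pairing of legs

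*Combined protocol and SAP*

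**What the plan says.** Section 4.4 says of the study as a whole that "this study is not aimed at hypothesis testing". It then sizes one comparison as a test, rest against the measurement directly after exercise, "using dependent sample T-test with an expected effect size of 0.4", alpha 0.05 and power 0.9. The result is that "we would require 68 samples". Each exercise session yields one usable measurement site, so the section adds a second session: "all participants will undergo two exercise sessions", which it counts as 2 x 35 = 70.

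Section 5.1 shows where the second set of 35 comes from: "The treadmill exercise and the corresponding measurements will be performed twice to include measurements of both legs". The same section assigns the post-exercise measurements to a single observer.

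On the analysis, section 10.2 says only: "This will be analysed using a dependent sample t-test". It does not name the unit of analysis for this endpoint. It mentions no averaging within a person, participant effect or clustered variance. The random subject effects in sections 10.1 and 10.2 belong to the ICC models.

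Two further statements bear on the point. Section 8.3 says "Exercise by means of a treadmill will be performed after all rest measurements have been performed". The Figure 1 legend in section 5 says "Randomization will determine whether the right or left leg is measured first".

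**The concern.** A dependent t-test deals with one kind of pairing, rest with post-exercise in the same leg. It does not deal with the second kind, two legs in the same person. The calculation behind 68 takes the differences as mutually independent, whereas the plan supplies 35 independent people with two differences each. The legs share a person, a visit, a treadmill protocol and an observer, so their changes may well be alike.

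If they are, there are two consequences:

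- Pooling the 70 differences, which is what the count of 70 implies, makes the standard error too small. P-values and any confidence interval for the exercise change are then too optimistic.
- A valid participant-level analysis of the same data has less power than stated.

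A related point concerns the baseline. All rest measurements come before both bouts, so the leg measured second is compared with rest after two bouts. Randomising leg order keeps leg from being confounded with bout. It does not remove a second-bout effect from a pooled mean.

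**Working it through.** **Inputs.** From section 4.4: effect size d = 0.4 per rest/post pair, alpha 0.05, power 0.9, 68 pairs required, 35 participants with two sessions each. Section 4.4 does not say whether the test is two-sided. The correlation r between the two legs' changes is not in the documents, so it is **assumed** over a range. Both legs are assumed to have the same mean and SD of change.

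**Step 1. Reproduce the plan's figure.** Power of a paired t-test on n independent differences comes from the noncentral t distribution with n − 1 degrees of freedom and noncentrality d√n.

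- n = 68, two-sided: noncentrality 0.4 × √68 = 3.298, power 0.902. This is the smallest n that reaches 0.9, so 68 reproduces exactly. A one-sided test would need only 55.
- n = 70: power 0.910.
- n = 35 (one leg analysed alone): power 0.633.

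The plan's 68 is therefore the two-sided figure for independent pairs.

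**Step 2. Allow for two legs per person.** If each leg's change has variance σ², the mean of the two has variance σ²(1 + r)/2. A t-test on 35 participant means then has

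- effect size 0.4 / √((1 + r)/2), with 34 degrees of freedom;
- equivalent number of independent pairs 70 / (1 + r).

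For example, at r = 0.5 the effect size is 0.4 / √0.75 = 0.462, the noncentrality is 0.462 × √35 = 2.73, and power is 0.756. The equivalent number of pairs is 70 / 1.5 = 46.7.

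**Step 3. Error rate if the 70 differences are pooled.** The pooled test uses σ/√70 as its standard error, but the true value is σ√((1 + r)/70). The actual two-sided error is then about 2 × (1 − Φ(1.96/√(1 + r))). At r = 0.5 this is 2 × (1 − Φ(1.60)) = 0.110. Simulation under no effect (100,000 runs per r) is shown beside the formula.

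| Assumed r | Equivalent pairs (68 needed) | Participant-level power, n = 35 | Pooled error, formula | Pooled error, simulated | People needed for 0.9 |
|---|---|---|---|---|---|
| 0 | 70.0 | 0.902 | 0.050 | 0.051 | 35 |
| 0.1 | 63.6 | 0.873 | 0.062 | 0.061 | 39 |
| 0.3 | 53.8 | 0.814 | 0.086 | 0.083 | 45 |
| 0.5 | 46.7 | 0.756 | 0.110 | 0.112 | 52 |
| 0.7 | 41.2 | 0.703 | 0.133 | 0.134 | 58 |

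In the same simulation the test on participant means stayed between 0.049 and 0.052. A nominal 95% interval from pooled data covers one minus the pooled error: about 92% at r = 0.3 and 89% at r = 0.5.

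**Step 4. Where the claim starts to fail.** Participant-level power falls below 0.90 at r of about 0.006, but the fall is gradual: 0.893 at r = 0.03 and 0.887 at r = 0.05. Judged by equivalent pairs, 70 / (1 + r) ≥ 68 needs r ≤ 70/68 − 1 = 0.029.

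**The case against.** The strongest reply is that r may be small. It is the correlation of the changes, not of the levels. Section 8.1.2 compares each post-exercise value with the same observer's rest value, so differencing removes a person's stable level and any constant observer bias. What is left is measurement error plus any shared response to exercise. Section 2 expects a difference below 2%, so error could dominate. This is fair: nothing in the documents favours r of 0.3 to 0.7 over 0 to 0.1, and at 0.1 the loss is slight. But the documents do not support r = 0 either, and the 0.9 is stated without that condition.

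Second, section 4.4 disclaims hypothesis testing, the sample of 35 is set by the ICC calculation, and the exercise comparison is secondary with no decision rule. This limits the severity. It does not remove the point, because the same section gives alpha, power and a required number for a test and uses them to justify a second treadmill session for every participant.

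Third, extra false positives would count against the sponsor's expectation of little change, so the bias is not in its favour. That is true, but the error rate is still wrong.

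Fourth, the legs could be tested separately. That fits section 10.2 and protects the error rate, but it does not use 70 pairs, and its power is 0.633.

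Two limits should be kept. The power claim covers only the measurement directly after exercise. The plan also does not promise a confidence interval for this endpoint, so the coverage figures apply only if one is reported.

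**Conclusion.** The concern holds. The figure of 68 is correct for independent pairs, and 2 x 35 is 70, but those 70 are two legs from each of 35 people. The unconditional 0.9 is a property the design has only if r is about zero, and pooling gives error rates that are too high whenever r is positive.

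The size depends on the assumed r. At 0.1 the loss is small. From about 0.3 it is material: power near 0.8 or lower, and a pooled error rate of 8% or more. These figures rest on equal means and SDs of change in the two legs and on a two-sided test, which is the reading that reproduces 68. The second-bout effect has not been quantified.

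This should be fixed, but it affects a secondary endpoint of a pilot. The primary ICC is not affected by this point.

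**What to change.** **Section 10.2.** Name the participant as the unit of analysis for the exercise comparison. At each time point, test the per-participant mean of the two leg differences (n = 35). Alternatively, fit a linear mixed model to the leg differences with a random participant effect and fixed effects for leg and bout (first or second). The mixed model also shows any second-bout effect; the participant mean respects the pairing of legs but still averages over the two bouts.

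**Section 4.4.** Replace the unconditional 0.9 with an assumed r and the power that follows, keeping the present restriction to the measurement directly after exercise. For example:

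> For the measurement directly after exercise, with 35 participants and two legs each, power for an effect size of 0.4 at two-sided alpha 0.05 is 0.87, 0.81 or 0.76 if the between-leg correlation of the change is 0.1, 0.3 or 0.5. This power is accepted without enrolling more participants.

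**Cost.** Wording in two sections, with no change to conduct or enrolment. The price is giving up the 90% claim. If the sponsor prefers to keep 0.9, it would need about 39, 45, 52 or 58 people at r = 0.1, 0.3, 0.5 or 0.7.
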